Clearing the fog: Is Hydroxychloroquine effective in reducing Corona virus disease 2019 progression: A randomized controlled trial

Registration NO: ID: NCT04491994

Date: 15 May 2020

Study design, setting and participants: This single Centre, parallel open label randomized controlled trial was carried out during 10th April to 31st May 2020 at department of Pulmonology, Pakistan Emirates Military Hospital (PEMH) over 500 patients from both genders between 18-80 years of age. The study design was approved by institutional ethical review committee. The study population was comprised of patients from both genders with Mild confirmed COVID-19 after their written consent. The study protocol and approval documents are available online at ClinicalTrials.gov with trial number of NCT04491994.

Sample size calculation: Sample size was calculated using OPEN EPI with 5% level of Confidence and 80% power to detect a difference and enrolment ration 2:1 between intervention and control group, at a two-sided significance level of $\alpha=0.05$, of 7 days in the median time to clinical improvement between the two groups, assuming that the median time in the SOC group was 14 days and assuming 55% efficacy of HCQ in preventing disease progression and achieving viral clearance at day 7. Calculated sample size was 467, however we used a sample size of 500.

Enrolment procedure: During study period, 672 confirmed PCR positive cases were assessed for eligibility. 132 did not meet selection criteria and subsequently excluded. 540 patients were then enrolled and randomized. Further 20 patients were excluded from analysis as 15 withdrew consent and 5 became symptomatic before first dose of HCQ. During follow up 13 patients were found to be deviated from advised therapy and 7 were lost to follow up yielding a final study population of

500. **Figure 1** summarizes this process. Randomization rules were designed by [name] together with principal investigators and implemented by an independent statistician who was not involved in data analysis. Stratified random sampling was applied to stratify all eligible patients according to age, gender and comorbidities. Computerized random number generator was used and allocation was done in 2:1 sequence. Cards with each group assignment number randomly generated by computer were placed in sequentially numbered envelopes that were opened as the patients were enrolled

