Interventions: A total of 349 patients included in intervention group and 151 in control group. In Hospital, HCQ was given to patients after written consent and after considering its contraindications. Three hundred and forty-nine (349) patients were included in intervention group and given HCQ in addition to standard of care treatment. After 12 hours of randomization HCQ was given. Standard dose of HCQ was 400 mg by mouth twice a day for day one followed by 200 mg 12 hourly for next 5 days. The patients who did not give consent for treatment with HCQ or had a known allergy to HCQ or chloroquine or had another known contraindication to treatment with the study drug, including retinopathy, G6PD deficiency and QT prolongation served as controls. Controls were matched with participants on the basis of age, gender and co morbid and comprised of 151 patients. Standard of care (SOC) treatment comprised of daily oral Vit C (2gms), oral Zinc (50mg), oral Vit-D (alfacalcidol 1ug) and tablet Paracetamol (for body aches/fever), intravenous fluids, hemodynamic monitoring, and laboratory testing for SARS-CoV-2 and baseline blood parameters. Neither patients, nor investigators, nor statisticians were masked to treatment assignment. Lab staff who performed sampling for PCR, basic blood tests and other routine measurement were unaware of treatment information. Data regarding age, co-morbidities, history of contact with a positive patient, days since contact, duration of symptoms, PCR status

with date and base line labs/X-ray chest were recorded. Any patient with day 0 CRP greater than 6mg/dl, Absolute lymphocyte count (ALC) < 1000 or evidence of infiltrates on X-ray chest were excluded. Daily temperature, respiratory rate (RR) and resting O2 saturation with pulse oximetry were monitored in all patients during their hospitalization.

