Operational definitions: A case was considered confirmed on the basis of positivity of RT-PCR of combined Oropharyngeal and Nasopharyngeal swabs. Severity of disease was defined as per criteria designed by WHO¹¹. Mild disease meant Patients with uncomplicated upper respiratory tract viral infection having non-specific symptoms such as low-grade fever (fever < 100F for < 3 days), fatigue, body aches, cough (with or without sputum production), anorexia, muscle pain, sore throat, nasal congestion, anosmia, headache and rarely diarrhea, nausea, and vomiting. PCR sampling was done on day 7 and 14 of admission. Any chronic health condition for which patients were on prior treatment was considered as co morbidity. After start of treatment, development of fever > 101 F for > 72 hours, shortness of breath by minimal exertion (10-Step walk test), derangement of basic lab parameters (ALC < 1000 or raised CRP) or appearance of infiltrates on CXR during course of treatment was labeled as progression irrespective of PCR status. PCR status of patients was checked after 7 days and 14 days of initiation of treatment.

Inclusion and exclusion criteria: Inclusion criteria included (1) Mild Corona virus disease (COVID-19) (2) PCR confirmed infection (3) Hospital admitted patients (4) 18-80 years age Exclusion criteria were (1) Moderate, severe and critical COVID-19 (2) day 0 CRP greater than 6mg/dl, ALC < 1000 or evidence of infiltrates on X-ray chest (3) comorbidity with life expectancy less than 6 months (4) Contraindications to HCQ therapy.

Outcomes: Primary outcome was disease progression within 5 days of start of treatment. This was defined by development of fever > 101 F for > 72 hours, shortness of breath by minimal exertion

(10- Step walk test), derangement of basic lab parameters (ALC < 1000 or raised CRP) or appearance of infiltrates on CXR. Patients underwent 6 hourly axillary temperature check, daily 10 feet walk test, daily Blood counts, CRP and X-Rays on day 0, 3 and 5.

Secondary outcome was Viral clearance. PCR negativity on day 7 and 14 after admission was recorded.

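### The primary composite mixes laboratory components measured by masked staff with dyspnoea and X-ray components that have no stated masking, and no planned analysis separates them

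*Combined protocol and SAP*

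**What the plan says.** All references are to the combined protocol and SAP.

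- **Design paragraph:** the trial is a "parallel open label randomized controlled trial".
- **Interventions:** "Neither patients, nor investigators, nor statisticians were masked to treatment assignment". The next sentence makes one exception: "Lab staff who performed sampling for PCR, basic blood tests and other routine measurement were unaware of treatment information".
- **Outcomes:** "Primary outcome was disease progression within 5 days of start of treatment". The clinical components are sustained fever and breathlessness on a walk test. The laboratory and X-ray part reads "derangement of basic lab parameters (ALC < 1000 or raised CRP) or appearance of infiltrates on CXR. Patients underwent", and the text goes on to a schedule of temperature checks, walk tests, blood counts, CRP and X-rays. Any one component makes the patient a progressor.
- **Operational definitions:** the same components are listed, including "shortness of breath by minimal exertion (10-Step walk test", and progression is declared whatever the PCR result.
- **Secondary outcome:** "PCR negativity on day 7 and 14 after admission was recorded".
- **Statistical analysis:** only the t-test and chi-square test are named. There is no component table, laboratory-only analysis or other sensitivity analysis.

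The document does not say who scored the walk test, who read the X-rays or who declared progression. It describes no masked reader or adjudicator.

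**The concern.** In an open-label trial, knowledge of the arm can influence outcomes that depend on judgement or self-report. Breathlessness on minimal exertion is felt and reported by a patient who knows the treatment. Whether a film shows a new infiltrate is a reading, and the plan states no protection for the reader. A lymphocyte count or CRP value produced by staff unaware of treatment is much less exposed.

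The plan pools both kinds of component into one binary outcome and tests only the pool. If a few more untreated controls than treated patients were called progressors on dyspnoea or X-ray, the result would look like a drug benefit. The pooled figure could not show whether that had happened, although the data needed to look into it were scheduled for collection.

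**Working it through.** **Sorting the components by stated protection**

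| Component | Stated protection from knowledge of arm |
|---|---|
| Lymphocyte count < 1000 | Measured by masked laboratory staff; numeric threshold |
| Raised CRP | Measured by masked laboratory staff; no threshold, so the call itself is not protected |
| Fever > 101 F for > 72 h | Numeric threshold, 6-hourly axillary readings; reader not named |
| Dyspnoea on walk test | Patient unmasked; scorer not named |
| X-ray infiltrates | Reader not named |

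The entry criteria exclude a day 0 CRP above 6 mg/dl, but the outcome definition does not say whether that or another value counts as raised. The walk test is given as 10 steps in one place and 10 feet in another. These passages need to be reconciled.

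**Size of the threat.** The plan gives no figure on this point to reproduce, and no control-arm progression rate.

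- From the document: 349 HCQ, 151 control, two-sided 0.05.
- Assumed: no drug effect, baseline risk b in both arms, and e net extra percentage points of progression in controls only. Net means that each extra call falls on a patient with no other qualifying component.

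For the pooled two-proportion z test, the chance of significance favouring HCQ is approximately Φ[(e − 1.96·s0)/s1], where

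- p̄ = [151(b+e) + 349b]/500
- s0 = √[p̄(1−p̄)(1/151 + 1/349)]
- s1 = √[(b+e)(1−b−e)/151 + b(1−b)/349]

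With b = 0.15 and e = 0.05:

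- p̄ = (30.20 + 52.35)/500 = 0.1651
- s0 = 0.0362 and s1 = 0.0377
- (0.05 − 1.96 × 0.0362)/0.0377 ≈ −0.55, and Φ(−0.55) ≈ 0.29

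Summing the exact binomial probabilities gives the same answer. Exact results:

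| Baseline | e = 0 | e = 2 points | e = 3 points | e = 5 points |
|---|---|---|---|---|
| 5% | 3% | 16% | 27% | 54% |
| 10% | 3% | 11% | 18% | 37% |
| 15% | 3% | 9% | 14% | 29% |
| 30% | 3% | 7% | 10% | 20% |

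With a continuity correction the 15% row becomes 7%, 11% and 24% for 2, 3 and 5 points. In patients, 2 to 5 points of 151 is 0.02 × 151 ≈ 3 to 0.05 × 151 ≈ 8 controls.

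**Laboratory-only test in the same scenario.** Assume 10 of the 15 baseline points are laboratory events, equal in both arms. The excess calls do not enter this test, and its chance of favouring HCQ is about 3%.

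**Price in power.** For a 55% relative reduction at 349/151, a laboratory-only endpoint has about 39% power at a 5% control rate, 63% at 10%, 80% at 15% and 91% at 20%. These rates are also assumed.

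**A tempting decision rule.** One could accept a composite benefit only if the laboratory result points the same way. Simulation at 15% baseline shows that this does little:

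- 5 extra points, laboratory share 10: false positives fall from 29% to 25%
- 5 extra points, laboratory share 5: from 29% to 21%
- 5 extra points, laboratory share 12: from 29% to 26%
- 3 extra points, laboratory share 10: from 14% to 13%

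Laboratory events are part of the composite, so when the composite is significant by chance they usually lean the same way.

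**The case against.** The strongest case against runs as follows.

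- **The laboratory data are used.** A reader might infer that no analysis uses them. That is not so, because lymphocyte count and CRP are inside the primary composite. Only an analysis that isolates them is missing.
- **The assessor is unknown.** A reader might infer that unmasked investigators judged dyspnoea and X-ray. The document does not say so, and the masked laboratory staff are also credited with further routine measurements whose scope is undefined. The supportable statement is that no masked assessor is stated. For dyspnoea the exposure remains whoever scored it, because the patient was unmasked.
- **The laboratory components are not fully masked outcomes.** Masking covers sampling and testing, not the person who labels a result as progression, and without a CRP cut-off that person has discretion. This stands, and it is why the fix needs a fixed cut-off.
- **PCR is already a protected outcome.** Its sampling was masked, but progression is declared regardless of PCR status. PCR therefore cannot show whether a difference in progression came from assessment.
- **The magnitude depends on chosen inputs.** This stands. Five net points on a 10% to 15% baseline is a 33% to 50% relative inflation of control events, and the figures fall at higher baselines or with a continuity correction.
- **Fever is also fairly objective.** It has a numeric threshold and thermometer readings, so it belongs in the component table in its own right.

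**Conclusion.** The concern holds in limited form. The primary composite combines components measured by masked staff with dyspnoea reported by unmasked patients and X-ray findings for which no masked assessor is stated. The plan provides no analysis to tell them apart, and one laboratory component has no cut-off.

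At an assumed 15% baseline with 2, 3 or 5 assumed extra points in controls, a nominal 2.5% chance of a false result favouring HCQ (about 3% by exact calculation) becomes about 9%, 14% or 29%. A laboratory-only test stays near 3%, provided the cut-offs are fixed and laboratory events are equal in the two arms. Both the baseline and the excess are assumptions.

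The documents do not show that biased assessment occurred, or that any composite result would be false. They show only that the plan could not distinguish such bias from a drug effect. This should be corrected: the exposure affects the primary claim and the remedy is cheap.

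**What to change.** 1. Add a supportive analysis of progression within 5 days restricted to lymphocyte count < 1000 or CRP above one stated cut-off, applied identically to both arms. Report the risk difference with a 95% CI.
2. Add a table of every qualifying component (fever, dyspnoea, lymphocyte count, CRP, X-ray) by arm.
3. State that a composite benefit carried mainly by dyspnoea or X-ray will be described as open to assessment bias. Do not make the claim depend on the laboratory result pointing the same way, since that rule gives little protection and could falsely reassure.
4. State who scored the walk test, read the X-rays and declared progression, and whether they knew the arm.
5. The text already reports final arm sizes. If the analysis is defined after the data were seen, label it post hoc.

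**Cost:** one table and one comparison on blood counts and CRP already scheduled in all patients, with no extra staff. The supportive analysis has fewer events and less power, so a null result there would not refute the composite. It addresses assessment bias only, and leaves other sources of bias untouched, such as how the control group was formed.

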Statistical analysis: Statistical interpretation of data was performed using Statistical Package for Social Sciences (SPSS) version 23. Results were expressed as mean, standard deviation (\pm SD) for all continuous variables and frequency and percentage for categorical data. We used t-test and chi-square test as appropriate to the nature and distribution of the variables. A p-value < 0.05 was considered statistically significant.

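### Recorded illness timing has no planned use in the fixed-day viral clearance comparison: this costs precision if allocation was random, and may bias the result if controls arose as Interventions describes

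*Combined protocol and SAP*

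**What the plan says.** All references are to the combined protocol and SAP.

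- **Outcomes**: the secondary outcome is viral clearance, and "PCR negativity on day 7 and 14 after admission was recorded". **Operational definitions** gives the days of admission as the clock in one sentence and the start of treatment in another: "PCR status of patients was checked after 7 days and 14 days of initiation of treatment".
- **Inclusion and exclusion criteria**: the inclusion list is "1) Mild Corona virus disease (COVID-19) (2) PCR confirmed infection (3) Hospital admitted patients (4) 18-80 years age". Neither it nor the exclusion list limits symptom duration or the age of the positive swab. The only duration in the definition of mild disease concerns fever: "low-grade fever (fever < 100F for < 3 days".
- **Interventions**: baseline recording includes "history of contact with a positive patient, days since contact, duration of symptoms, PCR status", with the PCR date. No repeat swab at day 0 is listed.
- **Enrolment procedure**: the plan is to "stratify all eligible patients according to age, gender and comorbidities" and then allocate 2:1 by computer-generated numbers in sequential envelopes. **Interventions** instead says that the controls were patients who declined HCQ or could not take it, matched on the same three kinds of factor.
- **Statistical analysis**: "We used t-test and chi-square test as appropriate to the nature and distribution of the variables". No covariate model is mentioned.

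**The concern.** If the chance of a negative swab rises with time since infection, a patient admitted late with an old positive swab may be close to clearing on arrival, while one admitted at onset has further to go. Both are read on the same study day. The documents do not state this premise, but it is a reasonable one.

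Illness stage probably varied at entry. Symptom duration was worth recording, and among the post-randomization exclusions "15 withdrew consent and 5 became symptomatic before first dose of HCQ", which suggests that some patients entered before symptoms.

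Two things are at stake. A prognostic variable already in hand is left out, which costs precision. And if the arms differ in stage for a systematic reason, the crude comparison credits or charges that difference to HCQ. The same variable plausibly bears on the primary outcome, 5-day progression, although no size was worked out for that.

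**Working it through.** The plan gives no figure on this point to reproduce. From the documents come the arm sizes (349 and 151), two-sided alpha of 0.05 and the chi-square test. Everything else below is assumed.

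**1. Chance imbalance under randomization.** The standard error of the arm difference in mean illness time is SD × √(1/349 + 1/151) = 0.0974 × SD. For SDs of 2 to 5 days, the 95% limits (1.96 × SE) are about ±0.4 to ±1.0 day. If illness day at admission is uniform on 1 to 10, SD = √(99/12) = 2.87 and SE = 0.28 day. A 1-day difference is then 1/0.28 ≈ 3.6 standard errors, with two-sided probability of about 0.0004.

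**2. Precision under randomization.** Model: logit P(negative at day 7) = a + b × illness day + ln(1.8) × HCQ. Illness day is uniform on 1 to 10, and a is set so that 40% of controls are negative. Simulated results:

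| Slope b | Odds ratio, day 10 vs day 1 (exp(9b)) | Power, chi-square | Power, adjusted logistic | Gain (points) |
|---|---|---|---|---|
| 0.2 | 6 | 80% | 83% | 3 |
| 0.3 | 15 | 72% | 79% | 7 |
| 0.4 | 37 | 64% | 75% | 11 |

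Repeat runs agreed within 1 to 2 points. With no drug effect and balanced arms, the crude test rejected about 5% of the time, so it is valid.

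**3. Effect of a systematic difference, same model.** Moving one arm by 1 day shifts crude clearance by 4.5, 6.3 or 7.5 points for the three slopes. With no drug effect, the crude test then rejects about 16%, 25% or 35% of the time, against about 5% after adjustment.

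**4. A second model.** Let the probability of remaining positive t days after onset be S(t) = exp(−ln 2 × (t/m)^k). A patient who is positive at admission on illness day A is negative 7 days later with probability 1 − S(A+7)/S(A). With m = 14 and k = 2:

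- A = 4: 1 − exp(−0.6931 × (121 − 16)/196) = 31.0%
- A = 5: 1 − exp(−0.6931 × (144 − 25)/196) = 34.3%

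One day is thus worth about 3 points. With mean 4 and SD 3 days from onset to admission and no drug effect, the simulated false-positive rates are:

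| Arm difference (days) | Crude test | Adjusted for illness time |
|---|---|---|
| 0 | 5.5% | 5.4% |
| 1 | 9.7% | 4.2% |
| 2 | 28.8% | 6.3% |
| 3 | 52.7% | 5.9% |

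For m from 10 to 20, k from 1.5 to 3 and differences of 1 to 3 days, the false difference runs from 1 to 22 points and the crude false-positive rate from 6% to over 99%. With k = 1 (constant clearance hazard), S(A+7)/S(A) does not depend on A and there is no distortion.

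**The case against.** A reader might infer that fixed reading days and unused timing data in themselves mix stage of infection with the HCQ effect. The documents do not support that. Enrolment procedure describes computer-generated 2:1 allocation. If it was carried out, stage is balanced in expectation, the crude test keeps its 5% error, and a 1-day imbalance is a 3.6-standard-error event. The shifts in steps 3 and 4 are then not expected distortions. This part of the objection stands.

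The precision gain also rests on assumed inputs. The larger gains need steep gradients; at the shallowest slope the gain is only about 3 points, and it concerns a secondary outcome. The day-0 limits on CRP, lymphocyte count and infiltrates, together with the fever duration in the definition of mild disease, may narrow the spread of stage. This stands as a limit on size, not as a reason to ignore the data.

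Finally, if the controls were patients who refused or could not take HCQ, the main defect is non-random allocation. Such patients may differ in more than illness day, so adjustment for timing would be a partial remedy at most. That also stands.

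Nor do the documents show that the timing data were never examined. They specify no use, and a baseline comparison may have been made.

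**Conclusion.** The point holds in two conditional parts. If randomization was carried out as Enrolment procedure says, the crude chi-square test is valid and leaving out illness timing costs precision: roughly 3 to 11 points of power for slopes of 0.2 to 0.4, given a uniform illness day of 1 to 10, 40% control clearance and a conditional odds ratio of 1.8. If controls arose as Interventions says, nothing in the design balances illness stage, and a stage difference may be read as a drug effect on clearance. Its direction and size cannot be known from the documents; the rates in steps 3 and 4 are illustrations.

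The two clocks for the PCR days add to the uncertainty, since time from admission to start of treatment may vary. In either case, adjusting for a baseline variable already recorded is worthwhile and has little downside.

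**What to change.** 1. State one clock for the day-7 and day-14 PCR readings, and reconcile the wording of Operational definitions and Outcomes.
2. Tabulate by arm symptom duration, days since contact and days since the qualifying PCR, with the number missing for each.
3. Add logistic regression (or Mantel-Haenszel) for PCR negativity at day 7 and at day 14, adjusted for symptom duration and days since the qualifying PCR. Give patients without symptom onset their own category. Do not substitute days since contact: contact and onset are different time origins, separated by incubation, and some patients will have no known contact.
4. Use the same illness-time covariate in the analysis of 5-day progression.
5. Label these analyses as sensitivity or post hoc if they are specified after data were seen. The text already reports final group sizes, so this probably applies.
6. Reconcile the accounts of allocation in Enrolment procedure and Interventions, and state that the adjusted analysis does not remove other confounding if allocation was not random.

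The cost is a few sentences in the plan, one table and one additional model per outcome. The variables are described as recorded, so no new patients are needed, but their completeness has to be checked.

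### One lymphocyte count below the entry limit of 1000 counts as progression, so ordinary fluctuation may add non-disease events that dilute the comparison or, if baseline counts differ between arms, bias it

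*Combined protocol and SAP*

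**What the plan says.** All references are to the combined protocol and SAP.

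- **Entry.** The exclusion criteria, and the end of the Interventions section, remove patients with "day 0 CRP greater than 6mg/dl, ALC < 1000 or evidence of infiltrates on X-ray chest". Every enrolled patient therefore has an observed day-0 ALC of at least 1000.
- **Event.** The Outcomes section states: "Primary outcome was disease progression within 5 days of start of treatment". One component is "derangement of basic lab parameters (ALC < 1000 or raised CRP"). The components are joined by *or*, so this one is sufficient alone. Operational definitions gives the same list.
- **Persistence.** The fever component requires duration: "development of fever > 101 F for > 72 hours". The ALC component has no duration, repeat or change-from-baseline requirement.
- **Schedule.** Outcomes lists "daily Blood counts, CRP and X-Rays on day 0, 3 and 5".
- **Allocation and analysis.** Stratification was by age, gender and comorbidities (Enrolment procedure). Statistical analysis names the t-test and chi-square test only. It gives no covariate adjustment, analysis by component or sensitivity analysis.
- **Masking.** The trial was open label, but "Lab staff who performed sampling for PCR, basic blood tests and other routine measurement were unaware of treatment information".

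**The concern.** When the entry limit is also the event limit, there is no margin between being eligible and having progressed. A patient admitted at 1020 who reads 980 once has fallen by 4% (40/1020) and is an event, even if the next count is back at baseline. Repeated counts give repeated chances to cross the line.

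Two consequences follow for the primary comparison:

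1. If the arms contain similar proportions of patients near 1000, chance crossings raise both event rates and pull the risk ratio and risk difference towards no effect.
2. If the proportions differ, the difference in day-0 ALC passes into the primary outcome as an apparent treatment difference. Nothing in the plan would detect or correct it.

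**Working it through.** **Inputs from the documents.** Limit 1000 at entry and as event; window 5 days; arms of 349 and 151; two-sided alpha 0.05; 80% power; 2:1 allocation; 55% efficacy; calculated sample size 467.

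**Inputs not in the documents (assumed).** Within-patient day-to-day CV 8–15%; population median ALC 1500–2000 with log SD 0.3; no true change over the window; control progression rate; 55% efficacy read as a risk ratio (RR) of 0.45.

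**Step 1. The plan's own figure.** The plan gives no figure for ALC noise. Its sample size of 467 cannot be reproduced from the stated inputs, because no control progression rate is given. With RR 0.45, 2:1 allocation and no continuity correction, a control rate of about 15–16% returns it (15.3% gives 468, 15.4% gives 465). I use 15.5% in Step 4 for illustration only.

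**Step 2. A patient with a known, constant true level μ.** The chance that one count is low is p = Φ((1000 − μ)/(CV × μ)). With k independent counts, P(at least one low) = 1 − (1 − p)^k. For μ = 1100 and CV 10%, p = Φ(−100/110) = 0.182, so five counts give 1 − 0.818^5 = 63% and two counts give 1 − 0.818^2 = 33%. Over CV 8–15%, with five counts:

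| True level | At least one < 1000 | Two consecutive < 1000 |
|---|---|---|
| 1050 | 80–90% | 24–39% |
| 1100 | 50–80% | 6–23% |
| 1200 | 9–51% | 0.1–6% |

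If daily counts are correlated (assumed 0.5), the 1100 row becomes 40–67% and 13–32%.

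**Step 3. The enrolled population (simulation, observed day-0 value at least 1000).**

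- Five independent counts: 1.5–18% of patients have at least one low count, and 0.4–5% have two consecutive low counts.
- Two counts (days 3 and 5): about 1–10% have at least one low count.
- Patients *observed* at about 1050 on day 0: about half to two-thirds have at least one low count if counts are independent, and about 45–61% with correlation 0.5. This is below the 80–90% in Step 2 because some of these patients have a true level above their day-0 reading.
- Patients observed at 1000–1100 are only about 1.5–7.5% of those enrolled.
- Wider assumptions (median 1500–2100, CV 10–20%, five counts) give about 1–22% overall.

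**Step 4. Dilution if the false-event rate q is the same in both arms.** The observed rate is p + (1 − p)q, so the risk difference shrinks by the factor (1 − q). With assumed rates of 15.5% and 0.45 × 15.5% = 7.0%, and arms of 151 and 349:

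| q | Control | HCQ | RR | Power |
|---|---|---|---|---|
| 0 | 15.5% | 7.0% | 0.45 | 82% |
| 2% | 17.2% | 8.8% | 0.51 | 75% |
| 5% | 19.7% | 11.6% | 0.59 | 66% |
| 10% | 23.9% | 16.3% | 0.68 | 52% |

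At q = 5%, power falls from 63% to 41% with a 10% control rate, and from 91% to 80% with a 20% control rate.

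**Step 5. Bias if q differs.** Suppose HCQ has no effect and the true rate is 15.5% in both arms, but q is 5% in controls and 2% on HCQ. The spurious difference is (1 − 0.155) × (0.05 − 0.02) = 2.5 percentage points in favour of HCQ. Reversing the two values of q reverses the sign.

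**The case against.** **The size is not in the documents.** This stands. The range runs from negligible to important, so the documents support saying that fluctuation may add events. They do not support saying that it does, or by how much.

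**An absolute limit is a legitimate definition of becoming lymphopenic, and some counts below 1000 are true falls.** This also stands. The concern covers only crossings due to fluctuation, and a confirmation rule would miss some brief true falls.

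**The schedule can be read two ways.** The listed days may govern the blood counts as well as the X-rays. Daily counts is the more natural reading, but on the other there are only two post-baseline values. The problem is then smaller but remains.

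**Stronger readings that a reader might infer, and that the documents do not support:**

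- *Most patients admitted near 1050 will be false events, at 80–90%.* That figure is for a true level of 1050. Patients are admitted on an observed value, for which the figure is lower.
- *False events are equal in both arms, so the effect can only be diluted.* Masked laboratory staff support equal measurement error. They do not ensure equal numbers of patients near 1000. The Interventions section says that patients who declined HCQ or had contraindications served as controls, so balance in day-0 ALC cannot be presumed.
- *Confirmation repairs the component in full.* A fall from 2800 to 1050 (63%) is not an event under either rule, and with serial correlation the gain from confirmation is smaller.
- *The primary definition should be replaced.* The text describes a completed trial with unmasked investigators and statisticians. Changing the definition now would be a post hoc choice with its own risk of bias.

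**Conclusion.** The concern holds in a limited form. It is established from the text that entry and event share the limit of 1000, that one low count suffices, and that no planned analysis adjusts for day-0 ALC or separates the components. It follows that chance crossings may add events unrelated to disease course, diluting a treatment effect if day-0 ALC is balanced and biasing it in either direction if it is not.

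The size rests wholly on the assumed ALC distribution and variability: about 1–18% of patients with five daily counts, and about 1–10% with two. At the low end the effect on the result is modest. At 5–10% it would matter: under the assumed 15.5% control rate, RR 0.45 would appear as 0.59–0.68. The point warrants additional analyses. It is not a reason to discard the primary outcome.

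**What to change.** 1. Keep the stated primary definition.
2. Adjust the progression analysis for day-0 ALC as a continuous covariate, for example by logistic regression, alongside the unadjusted chi-square result. This addresses baseline imbalance in ALC; it does not remove false events.
3. Add a sensitivity analysis that counts the ALC component only when two consecutive *available* counts are below 1000. On the days-3-and-5 reading, both counts must be low. State which schedule was followed.
4. Report progression by component and arm, so that readers can see how many events rest on ALC alone.

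**Cost.** Analysis and reporting wording only; no new sampling, since day-0 and follow-up counts are already scheduled. The sensitivity analysis will have slightly fewer events, and a first low count on the last day of the window stays unconfirmed. Label these analyses post hoc if they are added after the data were seen.
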